#### **10.5 Toxicity Monitoring and Stopping Rules**

All patients will be evaluable for toxicity and adverse events from the time of their first protocol treatment. Toxicity will be reported by type and severity according to the CTCAE version 4.0.

During the entire study period, toxicity will be closely monitored by the PI and clinical trial coordinator of this study, even though no formal stopping rules are stipulated in this protocol. In the event that toxicity is thought to be excessive for the study patient population at any point of the trial, the patient accrual to the trial will be suspended immediately, pending a review of all toxicity data. A final decision will be made by the PI and sponsor as to whether the trial should be amended, terminated or continue accrual. Such decision should be filed with and pre-approved by the institutional Protocol Monitoring Committee.

#### **10.6 Evaluation of Response**

All patients treated on the study must be assessed for response to treatment, even if there are major protocol treatment deviations or if they are ineligible. Each patient will be assigned one of the following categories: 1) complete response, 2) partial response, 3) stable disease, 4) progressive disease, 5) early death from malignant disease, 6) early death from toxicity, 7) early death because of other cause, or 9) unknown (not assessable, insufficient data). [Note: By arbitrary convention, category 9 usually designates the “unknown” status of any type of data in a clinical database.]

Patients in response categories 4-9 should be considered as failing to respond to treatment (disease progression). Thus, an incorrect treatment schedule or drug administration does not result in exclusion from the analysis of the response rate.

---

**11 Regulatory Considerations****11.1 Institutional Review Board/Ethics Committee approval**

The protocol for this study has been designed in accordance with the general ethical principles outlined in the Declaration of Helsinki. The review of this protocol by the IRB/EC and the performance of all aspects of the study, including the methods used for obtaining informed consent, must also be in accordance with principles enunciated in the declaration, as well as ICH Guidelines, Title 21 of the Code of Federal Regulations (CFR), Part 50 Protection of Human Subjects and Part 56 Institutional Review Boards.

The Investigator will be responsible for preparing documents for submission to the relevant IRB/EC and obtaining written approval for this study. The approval will be obtained prior to the initiation of the study.

The approval for both the protocol and informed consent must specify the date of approval, protocol number and version, or amendment number.

Any amendments to the protocol after receipt of IRB/EC approval must be submitted by the Investigator to the IRB/EC for approval. The Investigator is also responsible for notifying the IRB/EC of any serious deviations from the protocol, or anything else that may involve added risk to subjects.

Any advertisements used to recruit subjects for the study must be reviewed and approved by the IRB/EC prior to use.

**11.2 Informed consent**

The Investigator must obtain informed consent of a subject or his/her designee prior to any study related procedures as per GCPs as set forth in the CFR and ICH guidelines.

Documentation that informed consent occurred prior to the subject's entry into the study and the informed consent process should be recorded in the subject's source documents. The original consent form signed and dated by the subject and by the person consenting the subject prior to the subject's entry into the study, must be maintained in the Investigator's study files.

Amendment 5 Dated 03/02/2016

**11.3 Subject confidentiality**

Celgene affirms the subject's right to protection against invasion of privacy. In compliance with United States federal regulations, Celgene requires the Investigator to permit representatives of Celgene Corporation and, when necessary, representatives of the FDA or other regulatory authorities to review and/or copy any medical records relevant to the study in accordance with local laws.

Should direct access to medical records require a waiver or authorization separate from the subject's statement of informed consent, it is the responsibility of the Investigator to obtain such permission in writing from the appropriate individual.

**11.4 Study records requirements**

The Investigator must ensure that the records and documents pertaining to the conduct of the study and the distribution of the protocol therapy, that is copies of CRFs and source documents (original documents, data, and records [e.g., hospital records; clinical and office charts; laboratory notes; memoranda; subject's diaries or evaluation checklists; SAE reports, pharmacy dispensing records; recorded data from automated instruments; copies or transcriptions certified after verification as being accurate copies; microfiches; photographic negatives, microfilm, or magnetic media; x-rays; subject files; and records kept at the pharmacy, at the laboratories, and at medico-technical departments involved in the clinical study; documents regarding subject treatment and drug accountability; original signed informed consents, etc.]) be retained by the Investigator for as long as needed to comply with national and international regulations (generally 2 years after discontinuing clinical development or after the last marketing approval). The Investigator agrees to adhere to the document/records retention procedures by signing the protocol.

**11.5 Premature discontinuation of study**

The Principal Investigator, institution, Celgene, and Novartis have the right to discontinue this study at any time for reasonable medical or administrative reasons.

Possible reasons for termination of the study could be but are not limited to:  
Amendment 5 Dated 03/02/2016

---

- Unsatisfactory enrollment with respect to quantity or quality.
- Inaccurate or incomplete data collection.
- Falsification of records.
- Failure to adhere to the study protocol.

Any possible premature discontinuation would be documented adequately with reasons being stated, and information would have to be issued according to local requirements (e.g., IRB/EC, regulatory authorities, etc.).

## **12 Appendices**

**Appendix A:** Risks of Fetal Exposure, Pregnancy Testing Guidelines and Acceptable Birth Control Methods

### **Risks Associated with Pregnancy**

The use of lenalidomide in pregnant females and nursing mothers has not been studied nor has the effect of the lenalidomide on human eggs and sperm. Lenalidomide is structurally related to thalidomide. Thalidomide is a known human teratogenic active substance that causes severe life-threatening birth defects. An embryofetal development study in animals indicates that lenalidomide produced malformations in the offspring of female monkeys who received the drug during pregnancy. The teratogenic effect of lenalidomide in humans cannot be ruled out. Therefore, a risk minimization plan to prevent pregnancy must be observed.

All study participants must be registered into the mandatory REMS® program, and be willing and able to comply with the requirements of REMS®.

#### Criteria for females of childbearing potential (FCBP)

This protocol defines a female of childbearing potential as a sexually mature female who: 1) has not undergone a hysterectomy or bilateral oophorectomy or 2) has not been naturally postmenopausal for at least 24 consecutive months (i.e., has had menses at any time in the preceding 24 consecutive months).

#### The investigator must ensure that:

- Females of childbearing potential comply with the conditions for pregnancy risk minimization, including confirmation that she has an adequate level of understanding
- Females NOT of childbearing potential acknowledge that she understands the hazards and necessary precautions associated with the use of lenalidomide

---

- Male patients taking lenalidomide acknowledge that he understands that traces of lenalidomide have been found in semen, that he understands the potential teratogenic risk if engaged in sexual activity with a female of childbearing potential, and that he understands the need for the use of a condom even if he has had a vasectomy, if engaged in sexual activity with a female of childbearing potential.

#### Contraception

Females of childbearing potential (FCBP) enrolled in this protocol must agree to use two reliable forms of contraception simultaneously or to practice complete abstinence from heterosexual intercourse during the following time periods related to this study: 1) for at least 28 days before starting lenalidomide; 2) throughout the entire duration of lenalidomide treatment; 3) during dose interruptions; and 4) for at least 28 days after lenalidomide discontinuation.

The two methods of reliable contraception must include one highly effective method and one additional effective (barrier) method. FCBP must be referred to a qualified provider of contraceptive methods if needed. The following are examples of highly effective and additional effective methods of contraception:

- Highly effective methods:
  - Intrauterine device (IUD)
  - Hormonal (birth control pills, injections, implants)
  - Tubal ligation
  - Partner's vasectomy
- Additional effective methods:
  - Male condom
  - Diaphragm
  - Cervical Cap

---

Because of the increased risk of venous thromboembolism in patients with multiple myeloma taking lenalidomide and dexamethasone, combined oral contraceptive pills are not recommended. If a patient is currently using combined oral contraception the patient should switch to one of the effective method listed above. The risk of venous thromboembolism continues for 4–6 weeks after discontinuing combined oral contraception. The efficacy of contraceptive steroids may be reduced during co-treatment with dexamethasone.

Implants and levonorgestrel-releasing intrauterine systems are associated with an increased risk of infection at the time of insertion and irregular vaginal bleeding. Prophylactic antibiotics should be considered particularly in patients with neutropenia.

**Pregnancy testing**

Medically supervised pregnancy tests with a minimum sensitivity of 50 mIU/mL must be performed for females of childbearing potential, including females of childbearing potential who commit to complete abstinence, as outlined below.

**Before starting lenalidomide**

*Female Patients:*

FCCP must have two negative pregnancy tests (sensitivity of at least 50 mIU/mL) prior to prescribing lenalidomide. The first pregnancy test must be performed within 10-14 days prior to prescribing lenalidomide and the second pregnancy test must be performed within 24 hours prior to prescribing lenalidomide. The patient may not receive lenalidomide until the Investigator has verified that the results of these pregnancy tests are negative.

*Male Patients:*

Must agree to practice complete abstinence or agree to use a condom during sexual contact with pregnant females or females of childbearing potential throughout the entire duration of lenalidomide treatment, during dose interruptions and for at least 28 days following lenalidomide discontinuation, even if he has undergone a successful vasectomy.

Amendment 5 Dated 03/02/2016

**During study participation and for 28 days following lenalidomide discontinuation***Female Patients:*

- FCBP with regular or no menstrual cycles must agree to have pregnancy tests weekly for the first 28 days of lenalidomide treatment, including dose interruptions and then every 28 days throughout the remaining duration of lenalidomide treatment, including dose interruptions, at lenalidomide discontinuation, and at Day 28 following lenalidomide discontinuation. If menstrual cycles are irregular, the pregnancy testing must occur weekly for the first 28 days of lenalidomide treatment, including dose interruptions, and then every 14 days throughout the remaining duration of lenalidomide treatment, including dose interruptions, at lenalidomide discontinuation, and at Day 14 and Day 28 following lenalidomide discontinuation.
- At each visit, the Investigator must confirm with the FCBP that she is continuing to use two reliable methods of birth control at each visit during the time that birth control is required.
- If pregnancy or a positive pregnancy test does occur in a study patient, lenalidomide must be immediately discontinued.
- Pregnancy testing and counseling must be performed if a patient misses her period or if her pregnancy test or her menstrual bleeding is abnormal. Lenalidomide treatment must be temporarily discontinued during this evaluation.
- Females must agree to abstain from breastfeeding during study participation and for at least 28 days after lenalidomide discontinuation.

*Male Patients:*

- Must practice complete abstinence or use a condom during sexual contact with pregnant females or females of childbearing potential throughout the entire duration of lenalidomide treatment, during dose interruptions and for at least 28

---

days following lenalidomide discontinuation, even if he has undergone a successful vasectomy.

- If pregnancy or a positive pregnancy test does occur in the partner of a male study patient during study participation, the investigator must be notified immediately.

Additional precautions

- Patients should be instructed never to give lenalidomide to another person.
- Female patients should not donate blood during therapy and for at least 28 days following discontinuation of lenalidomide.
- Male patients should not donate blood, semen or sperm during therapy or for at least 28 days following discontinuation of lenalidomide.
- Only enough lenalidomide for one cycle of therapy may be prescribed with each cycle of therapy.

**Appendix B: ECOG Performance Status Scale**

SCORE	DESCRIPTION
0	Fully active, able to carry on all pre-disease performance without restriction.
1	Restricted in physically strenuous activity but ambulatory and able to carry out work of a light or sedentary nature, e.g., light house work, office work.
2	Ambulatory and capable of all self-care but unable to carry out any work activities. Up and about more than 50% of waking hours.
3	Capable of only limited self-care, confined to bed or chair more than 50% of waking hours.
4	Completely disabled. Cannot carry on any self-care. Totally confined to bed or chair.
5	Dead.

**Appendix C: Cockcroft-Gault estimation of CrCl**

Cockcroft-Gault estimation of creatinine clearance (CrCl):  
(Cockcroft, 1976; Luke 1990)

$$\text{CrCl (mL/min)} = \frac{(140 - \text{age}) \times (\text{weight, kg})}{72 \times (\text{serum creatinine, mg/dL})}$$

$$\text{CrCl (mL/min)} = \frac{(140 - \text{age}) \times (\text{weight, kg})}{72 \times (\text{serum creatinine, mg/dL})} \times 0.85$$

**Appendix D: Staging of Chronic Lymphocytic Leukemia****Modified Rai clinical staging system**

Risk	Stage	Description
Low	0	Lymphocytosis in blood or bone marrow
Intermediate	I	Lymphocytosis + enlarged lymph nodes
	II	Lymphocytosis + enlarged liver or spleen with or without lymphadenopathy
High	III	Lymphocytosis + anemia (Hgb <11 g/dL) with or without enlarged liver, spleen, or lymph nodes
	IV	Lymphocytosis + thrombocytopenia (platelet count <100,000/ $\mu$ L) with or without anemia or enlarged liver, spleen, or lymph nodes

**Binet Staging System**

Stage	Description
A	Two or less lymphoid bearing areas enlarged*
B	Three or more lymphoid bearing areas enlarged*
C	Presence of anemia (Hgb <10.0 g/dL) or thrombocytopenia (platelet count <100,000/microL)

\* Five lymphoid bearing areas are possible: cervical, axillary, inguino-femoral, spleen, and liver.

**Appendix E: Criteria for Treatment of CLL**

1. Weakness, night sweats, weight loss of  $\geq 10\%$  over a six month period, painful lymphadenopathy, or fever.
2. Symptomatic anemia and/or thrombocytopenia (Rai stages III or IV; Binet stage C)
3. Autoimmune hemolytic anemia and/or thrombocytopenia poorly responsive to corticosteroid therapy.
4. Progressive disease, as demonstrated by increasing lymphocytosis with a lymphocyte doubling time less than six months, and/or rapidly enlarging lymph nodes, spleen, and liver.
5. Repeated episodes of infection. Hypogammaglobulinemia without repeated episodes of infection is not a clear indication for therapy.

**Appendix F: NCIWG 2008 Response Criteria**

PARAMETER	CR*	PR*	PD*
Group A			
Lymphadenopathy†	None > 1.5 cm	Decrease $\geq$ 50%	Increase $\geq$ 50%
Hepatomegaly	None	Decrease $\geq$ 50%	Increase $\geq$ 50%
Splenomegaly	None	Decrease $\geq$ 50%	Increase $\geq$ 50%
Blood Lymphocytes	<4000/ $\mu$ L	Decrease $\geq$ 50% over baseline	Increase $\geq$ 50% over baseline
Marrow	Normocellular, <30% lymphocytes, no B-lymphoid nodules, Hypocellular marrow defines Cri (5.1.6).	50% reduction in marrow infiltrate or B-lymphoid nodules	
Group B			
Platelet count	>100 000/ $\mu$ L	> 100 000/ $\mu$ L or increase $\geq$ 50% over baseline	Decrease of $\geq$ 50% from baseline secondary to CLL
Hemoglobin	> 11.0 g/dL	> 11 g/dL or increase $\geq$ 50% over baseline	Decrease $\geq$ 2 g/dL from baseline secondary to CLL
Neutrophils‡	> 1500/ $\mu$ L	> 1500/ $\mu$ L or > 50% improvement over baseline	

Group A criteria define the tumor load, Group B criteria define the functions of the hematopoietic system (or marrow).

\*CR (complete remission): all of the criteria have to be met, and patients have the lack disease-related constitutional symptoms: PR (partial remission): at least two of the criteria of Group A plus one of the criteria of group B have to be met; SD is the absence of progressive disease (PD) and failure to achieve at least a PR; PD: at least one of the above criteria of Group A or Group B has to be met.

† Sum of the products of multiple lymph nodes (as evaluated by CT scans in clinical trials, or by physical examination in general practice).

‡ These parameters are irrelevant for some response categories.

---

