### 5.6 Concomitant therapy

#### 5.6.1 Recommended concomitant therapy

Subjects should receive full supportive care, including transfusions of blood and blood products, antibiotics, hematopoietic growth factors, analgesics, and antiemetics when appropriate.

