**5.6.1.6 Growth Factor Support**

Patients may receive growth factor support in the form of granulocyte colony stimulating factor (G-CSF), granulocyte macrophage colony stimulating factor (GM-CSF), or erythropoietin at the discretion of the treating physician.

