## **7 Response Criteria**

Baseline lesion assessments must occur within ≤ 28 days of protocol therapy initiation or as indicated in Section 2, Schedule of Study Assessments.

Efficacy assessments will be performed as delineated in Section 2, Schedule of Study Assessments Table.

Assessment for response will be made following the NCIWG 2008 CLL criteria for response (See Appendix F: NCIWG 2008 CLL Criteria for Response).

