**10 Statistical Considerations****10.1 Study Design/Endpoints**

This is a phase II, single institution, and non-randomized study of patients with untreated CLL/SLL, utilizing a two-stage trial design. The primary endpoint for this trial is the combined complete and partial response rate (at 3 months-the end of cycle 3) to the protocol therapy. We anticipate this trial will have a CR+PR response rate of at least 80%.

A two-stage design is employed for this trial. The null/unacceptable CR+PR response rate is  $\leq 60\%$  while the anticipated true response rate to the protocol treatment is at least 80% for each disease cohort. At the first stage, 26 patients will be accrued to the trial. If 15 or fewer of these patients respond, then the trial will be terminated early and the response rate to the protocol treatment will be deemed unacceptable ( $\leq 60\%$ ). Otherwise, if more than 15 patients respond during the first stage, an additional 19 patients will be enrolled to this trial during stage 2 for a total of 45 patients. If 32 or fewer of these 45 patients respond to the protocol treatment at the end of stage 2, no further investigation of the protocol treatment is considered warranted. On the other hand, if more than 32 patients out of the 45 enrolled patients respond, the protocol treatment will be considered promising. If the true response rate is  $\leq 60\%$ , the probability of ending the trial at stage 1 is 0.48. If, however, the true response rate is at least 80%, then the probability of ending the trial at stage 1 is only 0.01. This two-stage design has an overall alpha level of 0.045 and a power of 0.90.

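### Appendix F lets a transfused or growth-factor-supported blood count supply the one Group B criterion that a PR needs, which can only push the end-of-cycle-3 CR+PR count upward

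*Combined protocol and SAP*

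**What the plan says.** Section 10.1 sets the endpoint: "The primary endpoint for this trial is the combined complete and partial response rate (at 3 months-the end of cycle 3) to the protocol therapy". Section 7 says how it is scored: "Assessment for response will be made following the NCIWG 2008 CLL criteria for response", and points to Appendix F for those criteria.

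In Appendix F, Group A measures tumor load and Group B measures marrow function. The PR rule is "PR (partial remission): at least two of the criteria of Group A plus one of the criteria of group B have to be met". The Group B cells for PR are plain thresholds:

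- platelets above 100,000/µL, or up by at least 50%;
- hemoglobin "> 11 g/dL or increase" of at least 50%;
- neutrophils above 1500/µL, or "> 50% improvement over baseline".

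The table asks about cause only in the PD column, where a fall in platelets or hemoglobin must be due to CLL. The CR and PR columns have no counterpart.

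On supportive care, section 5.6.1 says "Subjects should receive full supportive care, including transfusions of blood and blood products, antibiotics, hematopoietic growth factors", among other measures, when appropriate. Section 5.6.1.6 adds: "Patients may receive growth factor support in the form of granulocyte colony stimulating factor (G-CSF), granulocyte macrophage colony stimulating factor (GM-CSF), or erythropoietin", at the treating physician's discretion. Section 5.6.2 prohibits other anti-cancer therapies but not blood products or growth factors. No section sets a support-free interval before the response assessment, and sections 7, 10.4 and 10.6 do not say how a supported count is classified.

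**The concern.** The Group B requirement is there to show that the marrow is working. A hemoglobin reached by transfusion or erythropoietin, or a neutrophil count reached on G-CSF, shows the effect of the support instead. Read literally, Appendix F accepts it.

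For CR and PR the error has one direction: support raises counts, so it can move a patient from stable disease to PR but not the reverse. The CR+PR count is compared with fixed limits (more than 15 of 26, then more than 32 of 45) against a fixed 60% null in a single-arm trial, so no control group shares the bias. What is at stake is the false-positive probability of the primary decision.

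**Working it through.** **Inputs.** From section 10.1: null rate 0.60, anticipated rate 0.80, 26 patients in stage 1, continue if more than 15 respond, 19 further patients, promising if more than 32 of 45 respond; stated alpha 0.045, power 0.90, early-stopping probabilities 0.48 and 0.01. From Appendix F: the PR rule and thresholds. From section 5.3.1: entry floors of 1000/mm³ neutrophils and 50,000/mm³ platelets, relaxed for extensive marrow involvement. From Appendix D: the Rai stages.

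**1. The plan's own figures.** With X ~ Bin(26, p) and Y ~ Bin(19, p):

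- P(stop at stage 1) = P(X ≤ 15)
- P(promising) = Σ over x = 16 to 26 of P(X = x) · P(Y ≥ 33 − x)

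At p = 0.60 these are 0.4787 and 0.0445; at p = 0.80 they are 0.0079 and 0.9001. The stated design reproduces (0.0445 against a printed 0.045 is rounding).

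**2. One patient through the table** (constructed for illustration). Baseline: platelets 60,000, hemoglobin 9.0, neutrophils 1,100. After cycle 3, nodes and blood lymphocytes have halved, so two Group A criteria are met. Unsupported counts:

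- platelets 65,000: below 100,000, and 65/60 = +8%, so not met;
- hemoglobin 9.4: below 11, and 9.4/9.0 = +4%, so not met;
- neutrophils 1,200: below 1,500, and 1,200/1,100 = +9%, so not met.

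Classification: stable disease. If G-CSF gives neutrophils of 2,000, or red cells or erythropoietin give hemoglobin of 11.2, one Group B line is met and the same disease scores as PR.

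**3. Who is affected.** The patient must meet at least two Group A criteria, not have PD, fail all three Group B lines unsupported, and receive support near the assessment that carries a count over a threshold. Stage alone does not define this group. In Appendix D, platelets below 100,000 make a patient stage IV, so a stage III patient has about 100,000 or more and will usually pass the platelet line unaided. A stage IV patient passes on hemoglobin above 11 or neutrophils above 1500. For CR, losing a supported value usually turns CR into PR, and both count in the endpoint; the count changes only if no unsupported Group B line is left.

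**4. Sensitivity.** The documents give no rate of supported counts at assessment. Assume that a fraction f of true non-responders is lifted to PR when the true rate is 60%. Then apparent rate = 0.60 + 0.40 f, and the expected extra PRs among 45 are 45 × 0.40 f.

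| f (assumed) | Apparent rate | Extra PRs in 45 | P(stop at stage 1) | P(promising) |
|---|---|---|---|---|
| 0 | 60% | 0 | 0.4787 | 0.0445 |
| 2.5% | 61% | 0.45 | 0.4369 | 0.0587 |
| 5% | 62% | 0.9 | 0.3955 | 0.0763 |
| 10% | 64% | 1.8 | 0.3157 | 0.1237 |

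**The case against.** The strongest reply is that section 7 invokes the NCIWG 2008 criteria as a whole. Appendix F is visibly an extract (it cites a subsection 5.1.6 that this protocol does not contain), and the full criteria may deal with supported counts. We cannot see that source. But Appendix F is the table to which section 7 sends the assessor. If the source has such a condition, the table has left it out; if not, the condition is missing. The same footnote is needed either way.

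The second reply is about reach, and much of it stands. Support is to be given when appropriate or at physician discretion, not without limit. Nothing in the protocol calls for support at the counts in the example: under section 5.5.3.5 a lenalidomide cycle may start with neutrophils of 500/mm³ and platelets of 25,000/mm³. Under section 5.1, CR, PR and stable disease all go on to cycle 4, so moving from stable disease to PR changes nothing in treatment. Failing all three Group B lines at once may be uncommon, and the 2.5% to 10% range comes from no passage. That one patient can tip a boundary is true of any misclassification in a two-stage design. These points limit the likely size; they do not supply the missing rule.

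**Conclusion.** The gap is real and lies in the definition of the primary endpoint. Applied as written, Appendix F can count as PR a patient who would be stable disease on unsupported counts, and for CR+PR the bias is only upward. The size is unknown and may be small. The design has little room for it: at a true rate of 60%, a one-point rise in the apparent rate already takes the false-promising probability above 0.05 (0.0587), and a four-point rise takes it to 0.1237. Those figures rest on the assumed fractions, not on trial data.

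A reader might infer more than the documents support:

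- **That support alone can produce a response.** It cannot; two Group A criteria are still required.
- **That stage III/IV patients in general are affected.** Appendix D and the thresholds show that the group is narrower.
- **That PFS is lengthened because support hides progression.** The PD cells for platelets and hemoglobin already have a causal qualifier, any other single criterion still triggers PD, and section 10.4 reports PFS only descriptively.
- **That the design calculations are wrong.** They reproduce.

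**What to change.** Add a footnote to Appendix F, for example: *For CR and PR, a Group B value counts only if it was obtained without platelet or red-cell transfusion (for platelets and hemoglobin), erythropoietin (for hemoglobin) or G-CSF/GM-CSF (for neutrophils) within the look-back window before the sample; a supported value counts as not met.* The study team should set the window length without reference to response results, and apply it from the concomitant therapies that the Schedule of Study Assessments records in cycles 1-12.

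The current text is Amendment 5 of March 2016, the protocol was final in June 2011, and planned accrual was about 1.5 years, so responses may already have been scored. If so, re-classify them under that window, or report a sensitivity analysis that counts support-dependent responses as non-responses.

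The cost is one footnote and a look-up in data already collected. Supportive care does not change. The observed response rate may be slightly lower, partly because a supported count that would have passed unaided is also set aside. If the anticipated 80% had included supported responses, which the documents do not say, a strict rate of 78% or 76% would put power at 0.826 or 0.729 instead of 0.900.
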